10.3.2.7. Complete Remission Rate

Complete remission rate is defined as rate of CR according to modified IWG AML response criteria per IRAC.

Number and percentage of subjects with complete remission will be summarized by treatment groups. Comparisons between AG-221 and CCR will be analyzed by Fisher's exact test. Investigator assessed results will be summarized as a supportive analysis

10.3.2.8. Hematologic Improvement Rate

Hematologic improvement rate is defined as rate of neutrophil response (hematologic improvement neutrophil response [HI-N]) + platelet response (hematologic improvement platelet response [HI-P]) + erythroid response (hematologic improvement erythroid response [HI-E]) according to IWG MDS HI criteria (Section 15.6).

Number and percentage of subjects with hematologic improvement will be summarized by treatment groups. Comparisons between AG-221 and CCR will be analyzed by Fisher's exact test.

Subjects who achieved post-baseline 56-day RBC transfusion independence, i.e., without RBC transfusion for at least 56 consecutive days post baseline during treatment exposure period, will be summarized by baseline RBC transfusion dependence status (Yes vs. No), within each category of best response (e.g., CR, CRi/CRp, PR/MLFS, SD, PD, etc.) and overall. Subjects with at least one transfusion during the baseline period (defined as within 56 days before the first dose date) are considered transfusion dependent at baseline. Time to transfusion independence will be summarized for the subject's first transfusion independence, and duration of the independence will be summarized using the transfusion independence with the longest duration experienced by a subject.

The post-baseline 56-day Platelet transfusion independence will be analyzed similarly.

10.3.2.9. Rate of HSCT

Rate of HSCT is defined as rate of bridge-to-HSCT through study treatment. This analysis is for the subjects who proceeded to a subsequent HSCT immediately after discontinuation of the study drugs. Subjects who received systemic anti-cancer therapy for AML after discontinuation of the study drugs and later underwent a subsequent HSCT are not included.

Number and percentage of subjects with HSCT will be summarized by treatment groups. Comparisons between AG-221 and CCR will be analyzed by Fisher's exact test. In addition, Numbers and percentages of subjects who with HSCT after reaching CR/CRi/CRp or without CR/CRi/CRp will be summarized.

10.3.2.10. Time to Treatment Failure

Time to treatment failure is defined as time from randomization to discontinuation of study treatment due to any cause. For BSC subjects, the duration is from randomization to the date of treatment discontinuation or the last visit date if still ongoing. For subjects received treatment other than BSC, the duration is from randomization to the last dose date or day before start of non-BSC treatment whichever occurs first; subjects who have completed the study treatment or are still active will be censored at last dose date.

The time to treatment failure will be analyzed using the KM method. The 25th percentile, median and 75th percentile time (including two-sided 95% CI) will be summarized for each treatment arm; the associated HR with two-sided 95% CI will be estimated using Cox proportional hazard models with and without stratification factors. A stratified and an unstratified log-rank tests will provide the pivotal p-value for the comparison between AG-221 and CCR arm.

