## Study Treatments

The options in the CCR treatment arm include:

- BSC only: continuous 28-day cycles of BSC. Best supportive care includes, but is not limited to, hydroxyurea for leukocytosis and/or differentiation syndrome associated with therapy of mutant IDH inhibition (ie, IDH differentiation syndrome), anti-infectives, analgesics, antiemetics, antipyretics, transfusions and nutritional support (refer to Section 7.1.5 and Section 8 for details);
- Azacitidine SC plus BSC: continuous 28-day cycles of azacitidine 75 mg/m^2/day SC for 7 days, plus BSC;
- LDAC SC plus BSC: continuous 28-day cycles of cytarabine 20 mg SC twice a day (BID) for 10 days, plus BSC;
- IDAC IV plus BSC: 28-day cycles of cytarabine 0.5 to 1.5 g/m^2/day IV for 3 to 6 days, per standard institutional practice, plus BSC; only BSC given after IDAC therapy concludes per standard institutional practice. (Note: any local standard regimen different from the above specification will need review and approval by the Medical Monitor.)

Subjects randomized to the AG-221 treatment arm will receive continuous 28-day cycles of AG-221 100 mg orally (PO) once a day (QD) for 28 days, plus BSC. Dose escalation to 200 mg may occur for augmenting treatment response (detailed in Section 7.2.1.2).

Study treatments as described above can continue until the End of Trial, unless discontinued for any of the reasons detailed in Section 11.1.

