**Table 2: Study Endpoints (Continued)**

Endpoint	Name	Description	Timeframe
Secondary (continued)	Duration of response	Time from the first documented MLFS/CR/CRi/CRp/PR to documented morphologic relapse, PD according to modified IWG AML response criteria ( Appendix F ) or death due to any cause, whichever occurs first	Up to ~ 49 months
		Time from the first documented CR/CRh to documented morphologic relapse, PD according to modified IWG AML response criteria ( Appendix F ) or death from any cause, whichever occurs first	Up to ~ 49 months
	Time to response	Time from randomization to first documented MLFS/CR/CRi/CRp/PR according to modified IWG AML response criteria ( Appendix F )	Up to ~ 49 months
		Time from randomization to first documented CR/CRh ( Appendix F )	Up to ~ 49 months
	Treatment mortality at 30 and 60 days	Rate of death from any cause within 30 and 60 days of initiation of study treatment	At 30 and 60 days after treatment start
	One-year survival	The probability of survival at 1 year from randomization	Up to ~ 49 months
	Overall remission rate	Rate of CR + CRi + CRp according to modified IWG AML response criteria ( Appendix F )	Up to ~ 49 months
	Complete remission rate	Rate of CR according to modified IWG AML response criteria ( Appendix F )	Up to ~ 49 months
	Hematologic improvement rate	Rate of HI-N + HI-P + HI-E according to IWG MDS HI criteria ( Appendix H )	Up to ~ 49 months
	Rate of HSCT	Rate of bridge-to-HSCT through study treatment	Up to ~ 49 months
	Time to treatment failure	Time from randomization to discontinuation of study treatment due to any cause	Up to ~ 49 months
	Safety and tolerability	Type, frequency, severity, seriousness and relationship of adverse events to study treatments; vital signs; ECG; clinical laboratory evaluations	Up to ~ 78 months

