### **7.2.3. Low-dose Cytarabine Treatment**

Subjects randomized to the LDAC treatment option will receive continuous 28-day cycles of cytarabine 20 mg SC BID for 10 days until the End of Trial, unless they are discontinued from the study treatment for any of the reasons detailed in Section 11.1. In addition, subjects may receive BSC per standard institutional practice and as deemed necessary by the investigator.

Before subjects commence each treatment cycle with LDAC, they should manifest adequate platelet and neutrophil recovery (ie, platelets and neutrophils should return approximately to baseline levels). Individual patients differ considerably regarding their ability to regenerate bone marrow cellularity after chemotherapy. In case of myelotoxicity with unacceptable cytopenia and poor regeneration 2 weeks after the last dose of LDAC, the start of the next treatment cycle can be delayed up to 2 weeks. In the event of prolonged (ie, more than 2 weeks) and severe (ie, Grade 4) neutropenia or thrombocytopenia, complicated by a Grade 4 infection or clinically significant bleeding, the duration of LDAC treatment can be reduced to 7 days, per investigators' discretion. The investigator should contact the Medical Monitor for guidance on LDAC dose modification, if needed.

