### **7.2.4. Intermediate-dose Cytarabine Treatment**

Subjects randomized to IDAC treatment option will receive 28-day cycles of cytarabine 0.5 to 1.5 g/m^2/day IV for 3 to 6 days, per standard institutional practice, unless they are discontinued from the study treatment for any of the reasons detailed in Section 11.1. In addition, subjects may receive BSC per standard institutional practice and as deemed necessary by the investigator. Subjects may only receive BSC if IDAC therapy concludes per standard institutional practice. (Note: any local standard regimen different from the above specification will need review and approval by the Medical Monitor.)

The dose of cytarabine should be calculated on Day 1 of each treatment cycle. Before subjects commence each treatment cycle with IDAC, they should manifest adequate platelet and neutrophil recovery as well as recovery of non-hematologic toxicities, per standard institutional practice. Treatment modification of IDAC due to toxicity should be performed according to Cytarabine UK SmPC or per standard institutional practice. The investigator should contact the Medical Monitor for guidance on IDAC modification, if needed.

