#### 9.6.2.2. Additional Secondary Efficacy Analyses

The other secondary endpoints include duration of response, time to response, rates of overall remission, CR and HI assessed by an IRAC according to modified IWG AML response criteria ([Appendix F](#)) and IWG MDS HI criteria ([Appendix H](#)), treatment mortality at 30 and 60 days, one-year survival, rate of HSCT and time to treatment failure. The definitions of these additional secondary efficacy endpoints are listed below and in Section 2.

**Duration of response** is defined as time from first documented MLFS/CR/CRi/CRp/ PR to documented morphologic relapse after CR/CRi/CRp/ PD or death due to any cause, whichever occurs first. Subjects without morphologic relapse, PD or death due to any cause will be censored at the date of the last response assessment.

**Time to response** is defined as time from randomization to first documented MLFS/CR/CRi/CRp/ /PR. Subjects without a MLFS/CR/CRi/CRp/ PR will be censored at the date of the last response assessment.

**Treatment mortality at 30 and 60 days** is defined as rate of death from any cause within 30 or 60 days of initiation of study treatment.

**One-year survival** is defined as the probability of survival at 1 year from randomization.

**Overall remission rate** is defined as rate of CR + CRi + CRp according to modified IWG AML response criteria ([Appendix F](#)).

**Complete remission rate** is defined as rate of CR according to modified IWG AML response criteria ([Appendix F](#)).

**Hematologic improvement rate** is defined as rate of neutrophil response (hematologic improvement neutrophil response [HI-N]) + platelet response (hematologic improvement platelet response [HI-P]) + erythroid response (hematologic improvement erythroid response [HI-E]) according to IWG MDS HI criteria ([Appendix H](#)).

**Rate of HSCT** is defined as rate of bridge-to-HSCT through study treatment.

**Time to treatment failure** is defined as time from randomization to discontinuation of study treatment due to any cause.

The rate of CR/CR with partial hematologic recovery (CRh; [Appendix F](#)) and duration of CR/CRh will be analyzed using the statistical methods mentioned above or other statistical methods as appropriate. Note: CRh is not available for the investigator's assessment and will be assessed by the Sponsor only and based on laboratory dataset.

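### Time to treatment failure ends at last dose for every treatment except BSC, against its own definition, and the event status of IDAC followed by BSC is open; separately, overall relative dose intensity exceeds 100% for fully compliant azacitidine and LDAC subjects

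*SAP*

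**What the plan says.** **TTF.** Protocol Table 2 gives the endpoint as "Time from randomization to discontinuation of study treatment due to any cause". Protocol 9.6.2.2 says that it "is defined as time from randomization to discontinuation of study treatment due to any cause", and SAP 10.3.2.10 opens with the same definition. That SAP section then sets two end dates. BSC subjects end at treatment discontinuation. For the rest, "For subjects received treatment other than BSC, the duration is from randomization to the last dose date or day before start of non-BSC treatment", whichever is earlier. Of these non-BSC subjects it adds: "subjects who have completed the study treatment or are still active will be censored at last dose date". It plans Cox hazard ratios and states that stratified and unstratified "log-rank tests will provide the pivotal p-value for the comparison between AG-221 and CCR arm". SAP Section 13, which lists changes from the protocol, names only the transfusion-independence analysis.

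**IDAC followed by BSC.** The Protocol Summary (Study Treatments) describes the IDAC option with "only BSC given after IDAC therapy concludes per standard institutional practice", and SAP 4.1 repeats this. Protocol 7.2.4 puts it differently: "Subjects may only receive BSC if IDAC therapy concludes per standard institutional practice".

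**RDI.** SAP 9.3 divides cumulative dose by duration of treatment, which SAP 9.1 counts from first to last dose. SAP 9.4 sets planned intensity per day of a 28-day cycle: 18.75 mg/m²/day for azacitidine and 14.3 mg/day for LDAC. For IDAC it builds planned intensity from the dose administered. SAP 9.7 uses RDI as the compliance measure.

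**The concern.** For a drug given on a few days per cycle, the last dose can precede the decision to stop by weeks; for a drug taken daily it normally does not. One rule written in terms of last dose therefore shortens TTF for azacitidine, LDAC and IDAC, and leaves BSC and uninterrupted AG-221 alone. Two arms that stop on the same schedule can then show different TTF, and the SAP attaches a hazard ratio and p-value to that comparison.

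The IDAC option adds a second gap. BSC after IDAC belongs to the assigned option, yet the SAP censors subjects who completed treatment without defining completion. Neither Protocol 11.1 nor SAP Section 6 lists completion among the reasons for treatment discontinuation.

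The RDI point has the same root, the missing final rest period, but a different consequence. It is descriptive, and it makes comparator compliance look better than it was.

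**Working it through.** **1. Rest days removed from TTF.** Dosing days D per 28-day cycle come from SAP 4.1: AG-221 28, azacitidine 7, LDAC 10, IDAC 3 to 6.

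- Stop at the end of an on-schedule cycle, cut = 28 − D: 0, 21, 18 and 22 to 25 days.
- Stop equally likely on any day, mean cut = Σ max(0, k − D)/28 over k = 1 to 28:
  - azacitidine 231/28 = 8.3 days
  - LDAC 171/28 = 6.1 days
  - IDAC 253/28 = 9.0 days (D = 6) to 325/28 = 11.6 days (D = 3)

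These are not upper limits. For LDAC, Protocol 7.2.3 says "the start of the next treatment cycle can be delayed up to 2 weeks", so a stop after such a delay gives 18 + 14 = 32 days. An AG-221 subject who stops after a dose hold (Protocol 7.2.1.2) also loses days.

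**2. Effect on the TTF comparison when there is no true difference.** The documents give neither the comparator mix nor the treatment durations. Assumptions: 158 per arm, 25% per comparator option, geometric number of cycles, stop day uniform on 1 to 28, unstratified two-sided log-rank test, mean Efron Cox log HR, 4,000 datasets per cell.

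| Rule and scenario | Mean 3 cycles | Mean 5 | Mean 8 |
|---|---|---|---|
| As written: HR; false positives | 0.92; 11.7% | 0.95; 7.7% | 0.97; 6.3% |
| Discontinuation date in all groups | 1.00; 5.1% | 1.00; 5.1% | 1.00; 5.2% |
| As written, AG-221 hold of 1–28 days before 25% of stops | 0.96; 5.9% | 0.98; 4.8% | 0.99; 4.4% |
| As written, such a hold before 50% of stops | 1.01; 4.5% | 1.01; 5.7% | 1.00; 4.8% |

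Repeat runs differ by about one percentage point. With 50% of comparators on BSC, false positives as written are 8.2%, 6.7% and 5.8%; with 10% on BSC, 14.4%, 8.4% and 6.4%.

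**3. IDAC followed by BSC.** Read literally, the TTF end date is the last IDAC dose. If the subject then counts as having completed treatment, that date is a censoring; if as having stopped, it is an event; if BSC is still assigned treatment, the subject has not failed. The text does not choose.

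**4. RDI.** The SAP's planned intensities reproduce: 75 × 7/28 = 18.75 mg/m²/day and 20 × 2 × 10/28 = 14.3 mg/day. A subject who takes every dose on time for n cycles has a duration of 28(n − 1) + D days, so:

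- azacitidine RDI = 525n/(28(n − 1) + 7)/18.75
- LDAC RDI = 400n/(28(n − 1) + 10)/14.3

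| Cycles | 1 | 2 | 3 | 6 |
|---|---|---|---|---|
| Azacitidine | 400% | 160% | 133% | 114% |
| LDAC | 280% | 147% | 127% | 112% |
| AG-221, uninterrupted | 100% | 100% | 100% | 100% |

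A two-cycle azacitidine subject on schedule reaches the top band (at least 90%) on 0.90/1.60 = 56% of planned dose. For a single IDAC cycle, the administered dose stands in both numerator and denominator and cancels, leaving 28/D whatever the dose. A dose reduction cannot show.

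**The case against.** The strongest case against is about size and consequence. TTF lies outside the OS–ORR–EFS sequence in SAP 10.1, and calling its p-value pivotal gives it no alpha. The rest-day effect is modest: only the three-cycle row is notable, and that row means stopping at about (3 − 1) × 28 + 14.5 = 70.5 days on average. Exponential stop times with medians of 2, 4 and 6 months (also assumed) give HR 0.94, 0.97 and 0.98. Last dose is an objective date in an open-label trial, and BSC has no last dose, so some difference in rules was unavoidable. All of this stands and limits the weight of the point. It does not remove the conflict with the definition.

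Three stronger readings are tempting.

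- **IDAC followed by BSC is left wholly undefined.** It is not: a date is given, and only event versus censoring is open. IDAC is the one drug option expected to conclude, so completion may be meant to cover it, but the section does not say so.
- **The bias must favour AG-221, perhaps heavily.** Counting the last IDAC dose as an event gives an HR of about 0.78, but only by assuming 25% on IDAC, at most two IDAC cycles and then BSC until discontinuation. None of these is in the documents. Censoring half of IDAC subjects as completed at their stop gives 1.04 to 1.11, against AG-221.
- **Stops at exact cycle ends produce large false-positive rates.** These are mainly an artefact of tied times. Protocol 11.1 lists reasons for stopping, not when stops fall, so the any-day pattern used here is itself an assumption.

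On RDI, days dosed, average daily dose and dose modifications (SAP 9.1, 9.5, 9.6) would still reveal under-dosing. By-cycle RDI need not be inflated for non-final cycles. AG-221 planned intensity follows the assigned dose, so prescribed AG-221 reductions may be equally invisible. SAP 9.4 gives no rule for combining IDAC cycles, so no multi-cycle IDAC figure is offered.

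**Conclusion.** Both points hold and should be corrected; neither touches OS, ORR, EFS or their alpha.

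The TTF derivation contradicts the definition in both documents, and the change is not declared. Under the assumptions above, with no AG-221 holds and no true difference, the HR is about 0.92 to 0.97 and false positives about 12% to 6%. Plausible holds bring the test back to about its nominal level. The documents therefore show a rule that is not neutral between arms, not a bias of known direction or size. Whether the end date for IDAC followed by BSC is an event or a censoring is open and could matter more than the rest days, by an amount the documents do not allow one to fix.

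The azacitidine and LDAC RDI results are arithmetic from the SAP's own formulas for subjects dosed in full and on schedule. They need no assumption about the comparator mix or when subjects stop.

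**What to change.** **TTF.** End it at the recorded treatment-discontinuation date in every group, as the SAP already does for BSC, and keep the last-dose version as a sensitivity analysis. Before database lock, reconcile the Protocol Summary, Protocol 7.2.4 and SAP 10.3.2.10 into one event-or-censor rule for IDAC followed by BSC, with the alternative readings as sensitivity analyses. That rule is a choice of estimand. It is still needed after the first change, because it decides which date counts as discontinuation for these subjects.

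**RDI.** Compute overall RDI as cumulative dose received divided by cumulative dose planned over the cycles started, truncated at death or data cut-off. For IDAC, take the planned dose from the regimen prescribed at cycle start where recorded; otherwise report RDI as not estimable. Substituting the SAP's duration of treatment exposure would not work: one full cycle would then score 28/34 = 82% for azacitidine, 28/37 = 76% for LDAC and 28/55 = 51% for AG-221.

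**Cost.** SAP wording and two derivations. Discontinuation is already registered (Protocol 6.2.3) and cycle start dates are already derived (SAP 5.1). There are two downsides. The discontinuation date depends on when an open-label decision is recorded, hence the last-dose sensitivity analysis. Under the new RDI a mid-cycle stop counts as missed doses, more so for AG-221 (three doses in cycle 1: 3/28 = 11%, against 3/7 = 43% for azacitidine), so RDI should be read beside duration of treatment.

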10.3.2.11. CR/CRh Rate

CR/CRh rate is the rate of CR or CRh where CRh is defined as partial hematologic recovery that achieves all criteria of CR except ANC and platelet criteria. For CRh, those criteria are:

- ANC > 0.5 x 10⁹/L; and

- Platelet > 50 x 10⁹/L

Number and percentage of subjects with CR/CRh will be summarized by treatment groups. Comparisons between AG-221 and CCR will be analyzed by Fisher's exact test.

CR/CRh assessed by IRAC only and using a sponsor derived assessment.

10.3.2.12. Duration of CR/CRh

Duration of CR/CRh is defined as time from first documented CR or CRh to documented morphologic relapse, PD, or death due to any cause, whichever occurs first. Subjects without morphologic relapse, PD, or death due to any cause will be censored at the date of the last response assessment.

The duration of CR/CRh will be analyzed using the KM method. The 25th percentile, median and 75th percentile time (including two-sided 95% CI) will be summarized for each treatment arm. Only subjects with CR/CRh response will be included and will be summarized for both IRAC and sponsor assessed responses.

10.3.2.13. Time to CR/CRh

Time to CR/CRh is defined as time from randomization to first documented CR/CRh.

Time to CR/CRh will be summarized with descriptive statistics in subjects with documented CR/CRh as determined by IRAC and sponsor assessment. It will also be summarized by cycle.

10.4. Subgroup Analysis

Appropriate subgroup analyses for primary and key secondary efficacy endpoints (ORR and EFS) by the following subgroups:

1. Age groups (≥ 60 years and < 70 years, ≥ 70 years and < 80 years, ≥ 80 years);
2. Gender (male and Female);
3. Region (North America, South America, Europe, Asia, Australia; US, non-US);
4. Race;
5. Prior systemic anti-cancer therapies for AML (2nd versus 3rd lines);
6. Baseline cytogenetic risk status (better-risk, intermediate-risk, poor-risk, failure);
7. IDH2 gene mutate type (R140 vs. R172);
8. AML initial diagnosis (primary or secondary);
9. WHO classification of AML;
10. ECOG performance status at baseline (Grade 0, 1, 2, 3);
11. Prior intensive therapy for AML (yes versus no) (IVRS and CRF source);
12. Primary refractory (yes versus no) (IVRS and CRF source);
13. Prior allogeneic HSCT for AML (yes versus no) (IVRS and CRF source);
14. ELN risk classification

15. Non-Protocol Definition Primary Refractory, defined as having at least 2 lines prior AML or Higher MDS treatment and never attained CR, Cri, or CRP (yes versus no).

A forest plot will be provided based on the HRs for each subgroup.

